6.1. ANALYSIS PLAN	10
6.2. SAMPLE SIZE ESTIMATES	11
7. DATA COLLECTION, HANDLING, AND STORAGE	12

Summary

This study seeks to investigate alternative strategies to hand hygiene (HH) and glove use in situations where glove use is required to perform health care activities in an effort to increase compliance with infection prevention efforts.

HH is the cornerstone of infection prevention. Despite the importance of and increased focus on HH, compliance remains low in healthcare settings (40% on average in a large meta-analysis). Insufficient time, high workload and under staffing are important barriers. Glove use, which is common and increasing, is another major barrier. New strategies are needed that improve time and efficiency particularly in settings where glove use is required (e.g. Contact Precautions). One area for further study is the requirement for HH prior to non-sterile glove use. This is a recommended practice with poor compliance that may be unnecessary. Furthermore, it may lead to reduced compliance with other recommended infection prevention practices, such as glove use. In this proposal we identify a novel strategy of directly gloving without performing HH prior to non-sterile glove use as a potential solution.

In this study we aim to perform a multicenter, cluster-randomized trial to evaluate the efficacy of direct gloving to improve compliance with infection prevention practices (i.e. HH and glove use). Herein, we will evaluate the safety and efficacy of directly gloving (compared to performing HH prior to glove use) and assess whether this strategy will lead to increased compliance with both HH and glove use. We previously demonstrated the safety of this strategy in a single-center randomized controlled pilot trial where we found no difference in bacterial contamination of gloves of healthcare providers who either performed or did not perform HH prior to donning non-sterile gloves. Thus, with potentially no added benefit and in a setting where we know that HH compliance is the lowest (i.e. prior to glove use), mandating HH prior to donning gloves as recommended in current guidelines could actually reduce both HH and glove compliance, placing patients at increased risk for developing infection.

Hypothesis 1: When compared to the standard practice of performing HH and then donning gloves, directly gloving when non-sterile gloves are indicated will increase compliance with HH and glove use and will have no effect on bacterial contamination of gloves (i.e. total bacterial colony counts).

Aim 1a: Perform a multicenter, cluster-randomized trial to evaluate the efficacy of a direct gloving strategy to improve compliance with infection prevention practices (i.e. HH and glove use).

Aim 1b: Perform a nested multicenter validation study, where gloved hands of healthcare providers will be randomly sampled to determine bacterial contamination of non-sterile gloves after donning.

1 Background Information and Rationale

1.1 Background Information

HH is the cornerstone of infection prevention. Despite the importance of and increased focus on HH, compliance remains low in healthcare settings (40% on average in a large meta-analysis). Insufficient time, high workload and under staffing are important barriers. Glove use, which is common and increasing, is another major barrier. New strategies are needed that improve time and efficiency particularly in settings where glove use is required (e.g. Contact Precautions).

One area for further study is the requirement for HH prior to non-sterile glove use. This is a recommended practice with poor compliance that may be unnecessary. Furthermore, because of the additional time required to cleanse hands and then don gloves, as well as the cumbersome nature of

applying gloves to recently cleansed hands, this practice leads to non-compliance with both HH and glove use – placing patients at risk. A recent randomized trial of 230 health care workers and demonstrated no difference in total bacterial colony counts or identification of pathogenic bacteria from the gloves of persons who either performed HH or did not perform HH prior to putting on non-sterile gloves ([name], PI, senior author). If unnecessary, HH before non-sterile glove use wastes valuable time, which might otherwise be spent engaged in direct patient care. And removing this unnecessary step may lead to increased compliance with infection prevention measures.

Existing guidelines are confusing and in some places contradictory and all support the need for further research to determine if HH before donning non-sterile gloves is a necessary step. The CDC supports the 2009 WHO HH Guidelines outlining expectations for appropriate HH. In general, the WHO teaches “Five Moments” of HH and uses this model to educate health care workers (HCW) on when HH should occur. This model is also used in surveillance when monitoring and reporting compliance with HH. The *WHO Glove Use Information Leaflet* (2009) under Part II, Section 7 - ‘Glove use and the need for HH’ states: “When an indication for HH precedes a contact that also requires glove usage, hand rubbing or hand washing should be performed *before donning gloves*”. Yet later in Section 23.1.3, it says: “Whether HH should be performed before donning non-sterile gloves **is an unresolved issue** and therefore this moment should not be recommended as an indication for HH”. Furthermore, the question “should HH be recommended before donning non-sterile gloves?” is highlighted within the WHO ‘HH Research Agenda’ Section.

1.2 *Rationale*

The necessity of HH before donning non-sterile gloves is unknown. Furthermore, because of the additional time required to cleanse hands and then don gloves, as well as the cumbersome nature of applying gloves to recently washed hands, this practice leads to non-compliance with both HH and glove use – placing patients at risk. As part of our pilot data for this grant, we performed a randomized trial of 230 HCWs and demonstrated **no difference** in total bacterial colony counts or identification of pathogenic bacteria from the gloves of persons who either performed HH or did not perform HH prior to putting on non-sterile gloves. If unnecessary, HH before non-sterile glove use wastes valuable time, which might otherwise be spent engaged in direct patient care. And removing this unnecessary step may lead to increased compliance with infection prevention measures. Despite the lack of supporting evidence, the WHO recommends that healthcare personnel perform HH before putting on non-sterile gloves and most hospital epidemiology and infection prevention groups routinely recommend this practice. Without this study, these non-evidenced based guidelines will persist as a barrier to HH and glove use leading to decreased compliance.

In Aim 1B, we will validate the findings shown by [name] (PI) et al. demonstrating **no difference** in total bacterial colony counts or identification of pathogenic bacteria from the gloves of persons who either performed HH or did not perform HH prior to putting on non-sterile gloves. Although the findings from the pilot study demonstrate the safety of this alternative strategy, these findings need to be replicated across multiple facilities and varying patient care areas (e.g. pediatrics, emergency departments). Further validation of the pilot findings, as well as results of Aim 1a, will demonstrate generalizability and support guideline/policy change and implementation.

REFERENCES:

1. Centers for Disease Control and Prevention. Guideline for Hand Hygiene in Health-Care Settings: Recommendations of the Healthcare Infection Control Practices Advisory Committee and the HICPAC/SHEA/APIC/IDSA Hand Hygiene Task Force. *MMWR*. Oct 25 2002;51(RR-16):1-45.

2. WHO Guidelines on Hand Hygiene in Health Care. 2009;
http://apps.who.int/iris/bitstream/10665/44102/1/9789241597906_eng.pdf.

1.3 Risks

Aim 1A: The research risks for this study are minimal. In this study, hospital units/wards will be recruited and randomized to either usual care or intervention; no individual patients or HCWs will be enrolled in this study. Preliminary data has demonstrated the safety of a direct gloving strategy (intervention). We hypothesize that by implementing an evidence-based strategy of directly gloving when hand hygiene is indicated will result in an overall improved compliance with infection prevention strategies of hand hygiene and glove use, thus minimizing risks and maximizing benefits. There is a possibility that hand hygiene may decrease in other situations, thus we will measure and monitor hand hygiene compliance at room entry and exit regardless of glove use. All data collected will be for the unit in aggregate and no HCW or patient identifying information will be collected.

Aim 1B: The risks for this aim of study will be minimal for study participants. Study participants are being asked to imprint their gloved hand on an agar plate after donning gloves during routine room entry. The predominant risk to participants in this study is the time required to participate, which will be less than 1 minute. HCWs will be instructed that they can decline participation without repercussion. No identifiable information will be collected from HCW participants. We will not be able to link HCW to individual HCW-patient interactions. Thus, the risk of a breach of confidentiality or privacy is very minimal.

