In order to account for differences in baseline compliance with infection control practices including HH and glove use, baseline rates of compliance will be observed across all available units (this includes 4 adult ICUs, 3 general pediatric wards units, 1 ED and 1 inpatient HD unit at UMMC and 4 adult ICUs and 1 ED at Shock Trauma). In the study period prior to randomization; the final units will be selected based on similar baseline compliance. For example, there are 11 general pediatric wards across three sites. Baseline data will be collected and compared across all 11 wards. One pediatric unit from each facility with the closest baseline composite HH and glove compliance rates will be selected. Thus we are matching 3 general pediatric wards (one from each site) based on pre-intervention outcomes of interest to improve power and minimize the impact of measured and unmeasured confounders. Once selected, the units will be randomized to the intervention or usual care group. This process will be done for each unit type (e.g. adult ICU).

The study will begin with a 6-month period of baseline data collection in which HH and infection prevention compliance will be recorded in all units that are potentially available for inclusion as described above. During that time period the investigative team will develop and refine educational, training and data collection tools. Following this baseline period, a short “wash-in” period of 3 months will be used to educate and train HCWs in the participating units regarding expected infection prevention practices of HH and glove use. The intervention period will be a full 12 months. This will allow the intervention to be tested over a full calendar year accounting for differences in seasonality as well as different levels of training across an academic year.

All participating units regardless of intervention status will receive education regarding policies and procedures for compliance with infection prevention strategies including HH and glove/gown use. This education will be identical in both groups (intervention and usual care) and will be consistent with published guidelines (WHO/CDC) with the exception of HH prior to donning non-sterile gloves - which according to existing guidelines is an uncertain area where research is needed. HCWs from units randomized to the usual care group will receive education that states that they should perform HH prior to donning non-sterile gloves. HCWs from units randomized to the

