intervention group will receive education that states that HH is not necessary prior to unsterile glove use. Both units will receive education around other necessary moments for HH and as stated this education will be identical for both groups.

Data collection in both the baseline and intervention phases will be as follows:

Primary Outcome:

Composite Compliance with expected infection prevention practices upon entry to Contact Precaution-patient rooms. HCWs in the usual care group will be recorded as compliant if HH AND glove use is observed at room entry; HCWs in the intervention group only need to have glove use observed to be considered compliant.

Secondary Outcomes:

1. Compliance with glove use upon entry to Contact Precaution-patient rooms for both groups
2. Compliance with HH upon entry to ALL patient rooms
3. Compliance with HH upon exit to ALL patient rooms

Additional Information collected will include: date, time and location (i.e. hospital/unit) of observation and the role of the HCW observed (e.g. MD, RN, other).

Note that all data collected is completely anonymous and no HCW identifying information will be collected nor reported

Aim 1B:

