4.1 Selection of Study population

Aim 1A. No individual HCW or patient participants will be enrolled in this study. In this cluster-randomized trial, hospital units will be selected for participation and randomized to either the intervention (direct gloving) or usual care strategies. Potential units for participation will include Adult ICU, General Pediatrics, Adult Emergency Department and Inpatient Hemodialysis Units at

the four participating hospitals (University of Maryland Medical Center, RA Cowley Shock Trauma Hospital, University of Iowa Hospitals and The Johns Hopkins Hospital). As outlined above, among the 43 possible units meeting this description, units will be selected for participation based on the results of baseline hand hygiene and glove compliance. 14 total units will be selected for study inclusion and will be randomized to either intervention or usual care. In each case, hospital leadership, unit leadership and the department of infection prevention will assent to unit participation. HCWs in each unit will be observed regarding compliance with hand hygiene and glove use; this data will be collected in aggregate for each unit and no individual healthcare worker data will be collected. This data is currently being collected at each facility as part of standard infection prevention practice.

Aim 1B. Individual HCWs from the above participating units will be randomly selected for participation. Individuals who consent will have samples taken of gloved hands after donning as outlined above.

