6.1 Analysis Plan

Aim 1A:

We will assess whether primary and secondary outcomes are significantly different in the experimental and usual care groups using the generalized estimating equations (GEE) approach with an unstructured working correlation matrix to adjust for clustering. We will perform multivariate analyses using GEE adjusting for covariates such as baseline compliance with HH and frequency of Contact Precautions. Analyses will be conducted at the level of the participating unit and will follow the intention to treat approach.

Aim 1B:

The primary analysis will be an intention-to-treat analysis where the gloved hands of HCWs sampled in the usual care group will be compared to those in the Intervention group regardless of HH activity. A secondary, as-treated analysis will be performed where HCWs who were observed to perform HH and then don gloves will be compared to those in which gloves were directly applied without performing HH. The primary, intention-to-treat analysis will provide great insight into the effectiveness of this intervention while the secondary, as-treated analysis will validate efficacy.

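### The analysis planned for hand hygiene (HH) can neither isolate an unintended fall in HH outside direct gloving nor show that such a fall is absent

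*Combined protocol and SAP*

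**What the plan says.** Section 1.3 (Risks, Aim 1A) names the hazard, a possible fall in HH in other situations, and gives the safeguard: "thus we will measure and monitor hand hygiene compliance at room entry and exit regardless of glove use".

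Section 3 (Study Design and Procedure, Aim 1A) lists three secondary outcomes: glove use on entry to Contact Precaution rooms, HH on entry to all patient rooms, and HH on exit from all patient rooms. Intervention units are taught that HH is not needed before non-sterile gloves; usual care units are taught that it is. The list of outcomes is introduced by "Data collection in both the baseline and intervention phases will be as follows". Between those phases, "a short “wash-in” period of 3 months will be used to educate and train HCWs in the participating units".

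Section 6.1 (Analysis Plan, Aim 1A) treats all these outcomes alike: "We will assess whether primary and secondary outcomes are significantly different in the experimental and usual care groups", by GEE, with adjustment for covariates such as baseline HH compliance. It gives no margin or decision rule for HH. The only margin in the document is the relative risk of 1.15 for glove contamination in Aim 1B.

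Section 4.1 adds, of unit HH and glove compliance: "This data is currently being collected at each facility as part of standard infection prevention practice".

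**The concern.** Two features of the plan prevent the HH outcomes from answering the question that section 1.3 raises.

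- **The entry outcome mixes two effects.** Omitting HH before gloves in a Contact Precaution room is the intervention itself. Omitting it where gloves are not involved is the feared spillover. Pooling all rooms adds the two together, so a fall in the pooled figure need not be spillover.
- **The test is not built to exclude a fall.** Failure to find a significant difference is compatible with no decline and also with a decline that the study was too imprecise to detect. The plan uses the appropriate logic for its other safety question, glove contamination, but not for this one.

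Section 1.2 says that the results of Aim 1A, with those of Aim 1B, are meant to support a change in guidelines. Whether direct gloving erodes HH elsewhere is something that readers of such a change will ask, and the planned analysis would leave it open.

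**Working it through.** **1. The mixing.** Let s be the share of entry observations made at Contact Precaution rooms, d_CP the fall in HH there and d_other the fall elsewhere. The pooled entry fall is

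s × d_CP + (1 − s) × d_other.

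With no spillover (d_other = 0) it is still s × d_CP. As an illustration, take HH before gloving at 40%, the lower end of the 40–50% in section 6.2. If intervention staff omitted it entirely, d_CP = 40 points, and a pooled fall of 5 points would appear once s = 5/40 = 12.5%. If half omitted it, d_CP = 20 points and s = 5/20 = 25%. The documents do not give s.

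**2. The plan's own power figure.** Section 6.2 gives no power for either HH outcome. The nearest figure is for glove use: 8 units, 500 observations each, ICC 0.01, a 10-point difference, power above 85%. With design effect 1 + 499 × 0.01 = 5.99, the effective number per arm is 4 × 500 / 5.99 = 334. A two-sided 5% normal-approximation test gives 84.9% (70 v 80%), 90.0% (75 v 85%) and 95.3% (80 v 90%). The stated figure is reproduced.

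**3. The same design effect applied to a fall in HH.**

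From section 6.2: 14 units, 500 observations per unit, alpha 0.05, ICC 0.001 and 0.01, HH 40–50%.

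Assumed: 7 v 7 allocation, a two-sided test, HH of 45%, all 500 observations usable for the outcome, no covariate adjustment, and a t reference on 14 − 2 = 12 df (critical value 2.179) because there are few clusters.

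- SE = sqrt(2 × 0.45 × 0.55 × (1 + 499 × ICC) / 3500)
- 95% CI half-width = 2.179 × SE
- Power from the noncentral t with noncentrality fall/SE

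| ICC | Design effect | SE | Half-width (points) | Power, 5-point fall | Power, 10-point fall |
|---|---|---|---|---|---|
| 0.001 | 1.499 | 0.0146 | 3.2 | 88% | >99% |
| 0.01 | 5.99 | 0.0291 | 6.3 | 35% | 88% |

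With HH at 40% or 50% and each arm's own variance, power for a 5-point fall is 88–90% at ICC 0.001 and 35–37% at ICC 0.01.

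**4. Reading a null result.** At ICC 0.01, an observed difference of exactly zero would carry an interval of about −6.3 to +6.3 points, so a fall of 6 points would remain compatible with the data. A true 5-point fall would be missed 100 − 35 = 65% of the time. At ICC 0.001 it would be missed 100 − 88 = 12% of the time.

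**The case against.** **The difference test suits the stated hypothesis.** Aim 1A expects HH and glove compliance to rise, and a test for a difference fits that. Aim 1B uses non-inferiority because its hypothesis is no effect. GEE will also give an estimate and an interval, and nowhere does the plan say that a null HH result will be read as no spillover. This stands in part: the test is not wrong for the hypothesis of Aim 1A. It does not, however, answer the separate question of harm that section 1.3 raises.

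**The precision may be better than shown.** At ICC 0.001 the problem is small. Five points is a reviewer's choice of fall. Units are selected for similar baseline compliance, randomisation is stratified, and section 6.1 adjusts for baseline HH. If baseline explained 50% of the between-unit variance (an assumption), power for a 5-point fall at ICC 0.01 would rise from 35% to about 51–54% (8–11 df); at 75%, to about 69–72%. This stands, and the figures above should be read as unadjusted. It does not touch the mixing of rooms or the absence of a decision rule.

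**Stronger readings that the documents do not support.**

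- A reader might infer that HH goes unseen in the wash-in and that a fall could run unnoticed for 3 + 12 = 15 months. The statement on phases concerns the study's own data collection. Section 4.1 says that each facility already collects these data routinely, so a fall could be seen and acted on outside the study. The absence of a named reviewer, schedule or threshold is missing detail, not evidence that nobody will look.
- A reader might see a conflict between section 1.3, which says that preliminary data showed safety, and section 1.2, which calls for replication. The sentence in section 1.2 itself opens by saying that the pilot demonstrated safety, and asks for replication to establish generalisability. The two sections agree.
- A reader might compute a confidence interval for the pilot to show that it did not establish safety. The documents give neither its group sizes nor its counts above 30 CFU, and the pilot findings they describe concern glove contamination, not HH elsewhere.

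**Conclusion.** The concern holds as a weakness of outcome definition and analysis. As written, the plan cannot separate intended omission from spillover in entry HH, and it has no rule by which a decline in HH could be excluded. The first defect holds at any ICC. The practical weight of the second depends on the ICC: on the stated unadjusted assumptions, a null result is fairly informative about a 5-point fall at 0.001 and uninformative at 0.01, though a 10-point fall would usually be detected at either. Fewer usable observations would widen the intervals; effective baseline adjustment would narrow them.

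This is a worthwhile and inexpensive improvement. It does not put the primary outcome in doubt, and it is not a finding that staff or patients would be left unprotected during the study.

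**What to change.** 1. In sections 3 and 6.1, define the spillover question separately. Analyse HH on exit from all rooms, and HH on entry to rooms not under Contact Precautions. The primary outcome already requires Contact Precaution rooms to be identified. Exit HH is the cleaner of the two, since gloves may also be worn on entry to other rooms. HH on entry to all rooms can stay as a descriptive outcome.
2. For both, report the difference between arms with a two-sided 95% CI. Conclude that there is no decrease only if the CI excludes a decline limit that the investigators fix before randomisation; otherwise report that spillover is not excluded.
3. As a minor clarification, state how the monitoring promised in section 1.3 will be done, for example from the routine facility data in section 4.1, including during the wash-in.

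**Cost.** Items 1 and 2 need analysis-plan wording and use observations already planned. A no-spillover conclusion becomes harder to claim: on the unadjusted figures at ICC 0.01, a limit tighter than about 6.3 points could not be excluded even if the observed difference were zero. The entry analysis also uses fewer observations than the all-rooms version, by an amount that the documents do not allow one to state. If item 3 leads to feedback to units, it could itself change HH, which is part of the usual care group's primary outcome. Giving both arms the same feedback would avoid unequal treatment but would not remove that effect.
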